8.1.5 Withdrawal due to Worsening of Clinical Status

An individual subject will be withdrawn from the study if he or she develops a condition or begins a therapy during the study period that would have excluded entry into the study (e.g., hypercapnia, acidosis, SICK score >2.4, hemodynamic instability, requirement of intubation or positive pressure ventilation, $SpO_2 < 90\%$ on oxygen). Additionally, the onsite pediatrician/Co-Principal Investigator may discontinue investigational device treatment at any time if she feels that further treatment puts the subject at unacceptable risk.

9 QUALITY CONTROL AND QUALITY ASSURANCE

The investigator agrees to be responsible for implementing and maintaining quality control and quality assurance systems to ensure that trials are conducted and data are generated, documented, and reported in compliance with the protocol, accepted standards of Good Clinical Practice, and all applicable federal, state, and local laws, rules and regulations relating to the conduct of the clinical study.

The investigator also agrees to conduct the study in an efficient and diligent manner and in conformance with this protocol; generally accepted standard of GCP; and all applicable federal, state, and local laws, rules and regulations relating to the conduct of the clinical study.

The investigator must allow study-related monitoring, audits, and inspection by the IRB/IEC, sponsor (or designee), government regulatory agencies, and, if applicable, University compliance and quality assurance groups of all trial-related documents and procedures.

The investigator shall prepare and maintain accurate study documentation in compliance with GCP standards and applicable federal, state, and local laws, rules and regulations.

10 DATA ANALYSIS METHODS

10.1 Determination of Sample Size

The target sample sizes for this study (up to 20 patients) are consistent with feasibility studies for other clinical interventions (Billingham et al., 2013).

10.2 Efficacy Variables

10.2.1 Signs of Inflammation in Children that can Kill (SICK) Score

The SICK score is a severity of illness score that incorporates vital signs, oxygenation (SpO₂), age, and physical examination information (mental status, capillary refill time) with associated weighting for each variable to provide a score from 1 to 7 (Kumar et al, 2003). The SICK score, which can be easily calculated, was initially intended to provide a severity of illness score to prioritize care for more sick children who needed urgent management in resource-limited settings. In resource-limited settings, the SICK score has paralleled clinical recovery or deterioration during therapy in hypoxemic children with respiratory illness (Turnbull et al, 2016).

10.2.2 Laboratory Efficacy Parameters

Laboratory efficacy parameters related to oxygenation will be collected by continuous monitoring of peripheral blood oxygen by pulse oximetry (SpO₂); continuous transdermal end-tidal carbon dioxide (CO₂) monitoring; capillary blood gases (e.g., SpO₂, PaO₂, PaCO₂, pH, base excess); and blood lactate.

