3 OBJECTIVES

The primary objective of this feasibility study is to collect preliminary information to aid in the design and conduct of future trials evaluating the safety and efficiency of a novel mask (nasal reservoir cannula) plus nasal cannula vs. nasal cannula alone for supplemental oxygen delivery in the treatment of hospitalized pediatric patients with hypoxemia due to severe pneumonia. This study is intended to provide information on intervention delivery and implementation, trial conduct, availability of patients and recruitment rates, protocol adherence, and effect sizes and outcomes to guide power calculation and design of a more definitive future study.

Our long-term goal is to conduct definitive studies to evaluate whether the addition of a novel mask (nasal reservoir cannula) to a standard nasal cannula during supplemental oxygenation is safe and more efficient (compared with standard nasal cannula alone) in reducing the total amount of oxygen needed per cylinder for adequate oxygen delivery in pediatric patients with hypoxemic respiratory illness in resource-limited settings.

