10.4 Oxygen Cylinder Use and Flow

The amount of oxygen (L) used from a cylinder and average oxygen flow (L/min) during Period 1 through 2 will be collected or calculated.

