10.5.5 Efficacy Analyses

Data will be summarized using descriptive statistics (number of patients, mean, median, standard deviation, minimum and maximum) for continuous variables and frequency and percentages of categorical variables. Tests of significance will be done only on an exploratory basis.

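### Oxygen use is missing from the efficacy variables and is summarised over both periods by treatment group, so the stated summaries do not yield the within-child device effect and SD needed for planning

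*Protocol*

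**What the plan says.** The study is meant to supply "effect sizes and outcomes to guide power calculation and design of a more definitive future study" (Section 3). The same section gives the question for the definitive studies: whether adding the mask is safe and more efficient "in reducing the total amount of oxygen needed per cylinder for adequate oxygen delivery in pediatric patients with hypoxemic respiratory illness". Section 5 repeats that aim.

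Section 10.2, on efficacy variables, has two parts. Section 10.2.1 is the SICK score. Section 10.2.2 opens with "Laboratory efficacy parameters related to oxygenation will be collected by continuous monitoring of peripheral blood oxygen by pulse oximetry" and continues with transdermal CO2, capillary blood gases (PaO2, PaCO2, pH, base excess) and lactate. Oxygen use is in neither part. It has its own Section 10.4: "The amount of oxygen (L) used from a cylinder and average oxygen flow (L/min) during Period 1 through 2 will be collected or calculated". The synopsis (Procedures) and Section 4.1, however, both mention cylinder oxygen in the efficacy paragraph.

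Section 10.5.1 summarises all variables descriptively for each treatment group. Section 10.5.5 adds the minimum and maximum, and states: "Tests of significance will be done only on an exploratory basis". Neither section names a within-child difference between devices. Section 10.1 sets the size at up to 20 children on precedent.

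**The concern.** The design is a randomised two-period crossover. Group A uses the mask plus cannula and then the cannula alone, and Group B the reverse. The information about the device lies in each child's difference between periods. The written analysis adds the periods together for oxygen use and then describes groups that have each used both devices.

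One declared output is therefore at stake: an effect size for oxygen use, with its variability, on which a later trial can be powered. The efficacy list also points away from that outcome. Section 2.3 describes a mask designed to give equal or higher FiO2 per litre of oxygen delivered, so a mask that works may show little difference in SpO2 or gases while flow falls. Equally, lower flow with lower SpO2 is not a saving. Flow and SpO2 need to be read together, and no section pairs them.

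**Working it through.** **Stated figure.** The only design number is up to 20 children. It rests on precedent, with no SD, effect size, alpha or power behind it, so there is no calculation to reproduce.

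**Which groups?** Section 4.1 randomises children to Groups A and B. Sections 10.5.3 and 10.5.4 summarise disposition and baseline characteristics by treatment group, which is informative for A and B. By device, it would describe largely the same children twice. A and B is thus the more natural reading. Section 7.2 does call the two devices treatments, so the other reading is possible and both are checked.

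**Reading 1: groups are A and B, oxygen over Periods 1 and 2.** Let M and C be a child's mean flow (L/min) on mask plus cannula and on cannula alone. Each period lasts 60 min.

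- Group A total = 60M + 60C.
- Group B total = 60C + 60M.
- Expected A minus B = 0, whatever M and C are. A period effect common to both groups also cancels.

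As an illustration only, take C = 2 L/min, which lies within the ranges quoted in Section 2.2, and the in vitro factor of 2.5 from Section 2.3, so M = 2/2.5 = 0.8 L/min.

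| | Group A (L) | Group B (L) | A minus B |
|---|---|---|---|
| Mask cuts flow 2.5-fold | 48 + 120 = 168 | 120 + 48 = 168 | 0 |
| Mask has no effect | 120 + 120 = 240 | 120 + 120 = 240 | 0 |

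Average flow over both periods behaves the same way: 168/120 = 1.4 L/min in each group, or 240/120 = 2 L/min in each. The group contrast does not distinguish the two cases.

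If the table were split by period as well, the device effect could be recovered as half of [(A1 − A2) + (B2 − B1)], where A1 to B2 are the group-by-period means. Its SD could not.

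**Reading 2: groups are the two devices.** The mean difference is available, but 10.5.1 and 10.5.5 give only an SD for each device. The SD of the within-child difference D is

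SD(D) = √(s_M² + s_C² − 2ρ·s_M·s_C),

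which needs the within-child correlation ρ, and that is not reported. With s_M = s_C = s (an assumption), SD(D) = s·√[2(1 − ρ)]. The document gives no ρ, so a range is shown. Future within-child sample size is proportional to SD(D)². The precision column uses 20 children, 10 per sequence, allowing for period: standard error = SD(D) × ½√(1/10 + 1/10) = 0.2236·SD(D). The t value on 18 df is 2.101, so the 95% half-width is 0.470·SD(D).

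| Assumed ρ | SD(D)/s | SD(D)²/s² | 95% half-width/s |
|---|---|---|---|
| 0 | 1.41 | 2.0 | 0.66 |
| 0.3 | 1.18 | 1.4 | 0.56 |
| 0.5 | 1.00 | 1.0 | 0.47 |
| 0.8 | 0.63 | 0.4 | 0.30 |

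From ρ = 0 to 0.8, the future sample size for a fixed difference varies by 2.0/0.4 = 5 times. The stated device summaries cannot narrow that range.

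**Are the data there?** Yes. Section 4.2.2 and Appendix A record flow and SpO2 every 15 min in each period, so per-period means and within-child differences can be computed for both.

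**The case against.** Oxygen use is not absent from the protocol. It has its own section, and the synopsis and Section 4.1 put it beside the efficacy measures. The comparison of mask plus cannula with cannula alone is named in the objective, and the future outcome is already stated. This is a descriptive feasibility study, and a statistical analysis plan may define the paired summary. All of that is fair, and it limits the point to the placement of oxygen use and the summary specified for it. It does not remove the point. The list in 10.2 disagrees with two other places in the same document, and an analysis plan that followed 10.2, 10.4 and 10.5.1 literally would inherit the gap.

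A reader might go further and infer that the planning effect could be picked after the fact from the eight variables in 10.2 and the two in 10.4, with an inflated false-positive rate. The documents do not support this. Tests are exploratory, no alpha or success rule is stated, and nothing suggests that the largest effect would be carried forward. A trial about oxygen needed could hardly be sized on base excess. Nor does it follow that the data would support opposite conclusions, because flow and SpO2 would both be reported.

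One caution stands against the remedy. The protocol states no rule for adjusting flow, the device brochure leaves flow to clinical judgment, and the study is open-label. Naming the contrast does not by itself give a clean estimate of efficiency, which is a further reason to report SpO2 beside it.

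**Conclusion.** The point holds as a gap in how oxygen use is classified and summarised. If treatment groups are A and B, the summary over both periods carries no device contrast. If they are devices, a mean difference can be read off, but its within-child SD and confidence interval cannot. In neither case do the stated summaries give the full planning input that Section 3 promises.

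The fivefold range in future sample size rests on equal SDs for the two devices, an assumed correlation of 0 to 0.8, and a future trial that also compares devices within children. For a parallel-group trial the SD by device would serve, but the confidence interval for the effect seen in this study would still need the within-child SD. The consequence is modest and recoverable, since the raw recordings exist. No error rate is breached, and the safety evaluation is not affected.

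**What to change.** In Section 10.2, list oxygen use per period: mean flow, and litres where measured. Align 10.4 with this by replacing the combined span with each period separately, and bring 10.2 into line with the synopsis and Section 4.1.

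In Section 10.5.5, state that the planning effect size is the within-child difference in oxygen use (mask plus cannula minus cannula alone), accounting for period and reported with its 95% CI, its SD and the number of children who contribute both periods. Report the same within-child contrast in mean SpO2 beside it, and say that lower flow is read as a saving only together with SpO2. Label the SICK score, CO2, blood gases and lactate as supportive. In 10.5.1, say whether treatment group means randomised sequence or device.

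The cost is a few sentences, with no new measurement or procedure. The small downside is less freedom to headline another variable.

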10.3 Safety Variables

Safety evaluations will include collection of adverse event, physical examination, vital sign, and clinical laboratory data. Hemoglobin rapid test, malaria rapid test, and blood glucose (point of care) will be obtained along with complete blood count (CBC), which may include hemoglobin, hematocrit, erythrocyte or red blood cell count (RBC), mean cell volume (MCV), segmented neutrophils, juvenile neutrophils, lymphocytes, monocytes, eosinophils, basophils, platelets, cell morphology, reticulocyte count.

Metabolic panel will be done based on local standard of care for patients with respiratory distress, but may include evaluation of

• Metabolic panel: Serum concentrations of sodium, potassium, chloride, total bilirubin, alkaline phosphatase, alanine transaminase (ALT), aspartate transaminase (AST), blood urea nitrogen (BUN), creatinine, glucose, total protein, albumin.

Safety evaluation will also involve the collection of data from: continuous transdermal endtidal carbon dioxide (CO₂) monitoring, capillary blood gases (P_aO₂, P_aCO₂, pH, base excess), peripheral blood oxygen saturation (SpO₂), and blood lactate.

10.4 Oxygen Cylinder Use and Flow

The amount of oxygen (L) used from a cylinder and average oxygen flow (L/min) during Period 1 through 2 will be collected or calculated.

10.5 Statistical and Analytical Plans

10.5.1 General Considerations

The full analysis population will include all randomly assigned subjects who have received study treatment. All variables will be summarized by descriptive statistics for each treatment group. The statistics for continuous variables will include mean, median, standard deviation, and number of observations. Categorical variables will be tabulated using frequencies and percentages.

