4 INVESTIGATIONAL PLAN

4.1 Summary of Study Design

The study is an open-label, prospective, feasibility study of hospitalized pediatric patients \geq 1 year and \leq 6 years of age with hypoxemia due to severe pneumonia. The primary objective of this feasibility study is to collect preliminary information to aid in the design and conduct of future trials evaluating the safety and efficiency of a novel mask (nasal reservoir cannula) plus standard nasal cannula vs. standard nasal cannula alone for supplemental oxygen delivery in the treatment of hospitalized pediatric patients with hypoxemia due to pneumonia in resource-poor settings. This study is intended to provide valuable information on the intervention delivery and implementation, trial conduct, availability of patients and recruitment rates, protocol adherence, and effect sizes and outcomes to guide power calculation and design of a more definitive future study.

Patients meeting entry criteria will receive baseline assessments followed by supplemental oxygen per standard of care. Patients will then be equally randomized to one of the two following groups:

- Group A: Each patient will receive oxygen for 1 hr using a novel mask (nasal reservoir cannula) plus standard nasal cannula (Period 1), followed by a subsequent 1-hr period of continued use of the standard nasal cannula delivery (Period 2).
- Group B: Each patient will receive oxygen for 1 hr using a standard nasal cannula (Period 1), followed by a 1-hr period of continued use of the novel mask (nasal reservoir cannula) plus standard nasal cannula (Period 2).

Patients with a body weight of 8-13 kg will receive treatment with a small 30 ml mask and patients with a body weight of 14-26 kg will receive treatment with a large 50 ml mask.

[figure not shown]

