5 DISCUSSION OF DESIGN

The study is an open-label, prospective, feasibility study of hospitalized pediatric patients with hypoxemia due to severe pneumonia. Patients meeting entry criteria will receive supplemental oxygen consistent with standard of care. Patients will be equally randomized to one of two groups. Group A will receive supplemental oxygen for 1 hr using a novel mask (nasal reservoir cannula) plus standard nasal cannula for 1 hr, followed by a 1 hr period using the standard nasal cannula only. Group B will receive treatment in the reverse order (treatment with standard nasal cannula alone for 1 hr followed by a 1-hr period of novel nasal reservoir cannula plus nasal cannula). Patients with a body weight of 8-13 kg will receive treatment with a small 30 ml mask and patient with a body weight of 14-26 kg will receive treatment with a large 50 ml mask.

The design of this study is consistent with the primary objective of collecting preliminary information to aid in the conduct of a more definitive trial evaluating the safety and efficiency of a novel nasal mask plus nasal cannula (vs. nasal cannula alone) in reducing the total amount of oxygen needed per cylinder for adequate oxygen delivery in pediatric patients with hypoxemic respiratory illness in resource-limited settings. Information on the feasibility of intervention delivery and implementation, trial conduct, availability of patients and recruitment rates, protocol adherence, and effect sizes and outcomes to guide future power calculations and designs will be of value in the design of future trials. The assessments used in this trial are standard assessments for the evaluation of pediatric patients with hypoxemia and severe pneumonia.

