7.2 Method of Assignment to Treatment

This is an open-label trial and each subject will sequentially receive supplemental oxygenation followed by sequential periods of both investigational treatment (nasal reservoir cannula plus nasal cannula) and standard of care treatment (supplemental oxygenation through nasal cannula alone). Patients will be randomized so that the order of initial treatment (nasal reservoir cannula plus nasal cannula vs. nasal cannula) is balanced between subjects. Patients with a body weight of 8-13 kg will receive treatment with a small 30 ml mask and patients with a body weight of 14-26 kg will receive treatment with a large 50 ml mask. All subjects will receive standard of care for their underlying disease according to WHO recommendations, including availability of standardized care of oxygen therapy.

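### Sections 10.4 and 10.5 summarise a two-period crossover by an undefined treatment group and state oxygen use over both periods, so the within-child device difference and its SD are never specified

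*Protocol*

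**What the plan says.** **Design.** Section 4.1 states "Patients will then be equally randomized to one of the two following groups": Group A has the reservoir plus cannula in Period 1 and the cannula alone in Period 2, and Section 5 adds that "Group B will receive treatment in the reverse order". Section 7.2 confirms that each child has "sequential periods of both investigational treatment (nasal reservoir cannula plus nasal cannula) and standard of care treatment". This is a randomised two-period, two-sequence crossover, and A and B are sequences.

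**Analysis.** Section 10.5.1 sets the unit of summary: "All variables will be summarized by descriptive statistics for each treatment group". Disposition (10.5.3), baseline characteristics (10.5.4), and duration of treatment and adverse events (10.5.6) use the same unit. Section 10.5.5 on efficacy reads "Data will be summarized using descriptive statistics (number of patients, mean, median, standard deviation, minimum and maximum) for continuous variables" and allows significance tests on an exploratory basis only. Section 10.4 gives the litres of oxygen used and the average flow across Periods 1 and 2, with no split by period or device.

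**Purpose.** Section 3 lists, among the things the study should deliver, "effect sizes and outcomes to guide power calculation and design of a more definitive future study".

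**The concern.** The unit of summary belongs to a parallel-group trial. Here each group contains one hour of each device, so a table by group over the whole study compares two orders of use, not two devices. Two places are most exposed. Oxygen use is the quantity the device is meant to reduce, and Section 10.4 states it across both periods. Adverse events are tabulated by treatment group, and a repeated event in one child is counted once. By sequence, such a table cannot show under which device an event occurred, although comparing the safety of the two delivery methods is part of what the study is meant to inform.

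The second matter is what the study hands on. If the next trial is again a crossover, its size depends on the SD of the within-child difference (reservoir plus cannula minus cannula alone). Section 10.5 names neither that difference nor its SD.

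**Working it through.** **Inputs from the protocol.** Two sequences with equal allocation (4.1). The sample size has no formula to reproduce, because 10.1 justifies it by precedent only: "The target sample sizes for this study (up to 20 patients) are consistent with feasibility studies for other clinical interventions". No alpha, power, SD or correlation is given. Flow is recorded every 15 minutes in each period (4.2.2). Bench flow is about 2.5 times lower with the reservoir, a ratio of 1/2.5 = 0.40 (2.3). Reservoir cannulas in general allow 25 to 50 percent lower flow, ratios of 0.75 to 0.50 (2.2).

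**Assumptions.** Cannula flow 2 L/min, within the 1 to 4 L/min quoted for older children in 2.2. Per-device SD s, and within-child correlation r of 0.5 to 0.8. For the sizing example: two-sided alpha 0.05, power 80%, and a difference of 0.5s.

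**1. Summary by sequence, periods combined.** Let μ be the cannula mean, δ the device effect and π the Period 2 effect, with no carry-over.

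- A: (μ + δ) in Period 1 and (μ + π) in Period 2; mean μ + (δ + π)/2.
- B: μ in Period 1 and (μ + δ + π) in Period 2; mean μ + (δ + π)/2.

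The A-minus-B contrast is 0 for any δ and any π. With μ = 2 and π = 0:

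| Flow ratio | True δ (L/min) | A: two-period mean | B: two-period mean | A − B |
|---|---|---|---|---|
| 0.40 | −1.2 | 1.40 | 1.40 | 0 |
| 0.50 | −1.0 | 1.50 | 1.50 | 0 |
| 0.75 | −0.5 | 1.75 | 1.75 | 0 |

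In litres at ratio 0.40, A uses 60 × 0.8 + 60 × 2.0 = 168 L and B uses 60 × 2.0 + 60 × 0.8 = 168 L. If carry-over into Period 2 differed by order (λ_A against λ_B), the contrast would be (λ_A − λ_B)/2, which is still not the device effect.

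**2. Summary by sequence and period.** The mean effect comes back. At ratio 0.40 the Period 1 contrast is 0.8 − 2.0 = −1.2, and the crossover estimate [(A1 − A2) − (B1 − B2)]/2 = [(0.8 − 2.0) − (2.0 − 0.8)]/2 = −1.2. With π = −0.2 it is [(0.8 − 1.8) − (2.0 − 0.6)]/2 = −1.2 again.

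**3. The SD under each reading.** The SD of the within-child difference is s√(2(1 − r)): 1.00s at r = 0.5 and √0.4 s = 0.63s at r = 0.8.

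- By sequence, periods combined: the table gives the SD of a two-period mean, s√((1 + r)/2).
- By sequence and period, or by device: the table gives s.

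Neither is the SD needed. It could be backed out only if the same variable were tabulated both ways, which the protocol does not ask for. A simulation with δ = −1.0, s = 0.8 and r = 0.7 agrees: both sequence means are 1.50, the SD of the two-period mean is 0.74, and the SD of the within-child difference is 0.62.

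**4. Effect on a future trial.** For a crossover, total N = [SD of difference × (1.96 + 0.84)/(0.5s)]².

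- Unpaired SD, √2 s: 63 children.
- Paired SD at r = 0.5: 32 children.
- Paired SD at r = 0.8: 0.4 × 31.4 = 12.6, so 13 children.

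Before rounding, the ratio is 2/[2(1 − r)] = 1/(1 − r), which is 2 at r = 0.5 and 5 at r = 0.8. A parallel trial needs s alone: 126 children in total for the same difference.

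**5. How well 20 children fix the SD.** With 18 degrees of freedom (20 children, two sequences), the 95% limits for an SD are 0.76 to 1.48 times the estimate.

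**The case against.** The strongest reply is that the protocol excludes nothing. *Treatment group* is undefined, and Section 7.2 uses *treatment* for the device condition, so the tables could be meant by device. Section 10.5.5 does not name the unit itself. Outcomes are recorded within each period, the exploratory tests may be paired, and a statistical analysis plan that is not shown may set out period adjustment and intervals. The child-level data will exist, so the paired SD can be computed at any time. Recruitment, adherence and delivery aims are untouched.

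Much of this stands. Reading the term as sequence is a strong inference, not a certainty. It is the only sensible reading for baseline and disposition, where every child is due to receive both devices, so a by-device reading elsewhere would give one term two meanings within Section 10.5. A reader might also infer that the plan cannot isolate the device effect at all. The documents do not support that: step 2 recovers it for anything recorded per period, and the zero contrast applies only when the periods are combined. Nor do they show that a future trial will be oversized. They do not say that it will be a crossover, and r has no source in them.

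The reply does not remove the point. The protocol positively names a summary unit that does not fit its design and states its oxygen variable over both devices. An analysis plan that followed this literally would inherit the problem, and reading the term as device still would not give the paired SD.

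**Conclusion.** The point holds in a limited form, as a should-fix. Followed literally, oxygen use and adverse events by sequence carry no device contrast; for two-period oxygen use the expected difference is 0 if there is no carry-over. For outcomes recorded per period, the mean device effect is recoverable. Under no reading is the SD of the within-child difference produced, which falls short of the aim in Section 3 if the next trial is a crossover. In that case only, and with r assumed at 0.5 to 0.8, sizing on the unpaired SD would inflate the trial 2 to 5 times. A heavier rating is not warranted, because the data needed are already collected and nothing is lost beyond repair.

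**What to change.** In Sections 10.4, 10.5.1, 10.5.5 and 10.5.6:

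- Define treatment as the device in use in the period.
- Report oxygen use, average flow, efficacy outcomes and adverse events by device and period, with each adverse event assigned to the period in which it began.
- Add, for each efficacy outcome and for oxygen use, the within-child difference (reservoir plus cannula minus cannula alone) with its SD, and a period-adjusted estimate with a 95% CI. Give the interval for the SD as well, since 20 children fix it only loosely.
- Keep tables by Group A and Group B for disposition and baseline, and call them sequences there.

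The cost is wording and one extra table. No new data, visits or patients are needed, because flow and the other outcomes are already recorded within each period.
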